### **2.3. Randomization and Masking**

Children meeting inclusion criteria will be enrolled by local trained study personnel. At enrollment, children will be assigned a study identification number using the next unassigned number on a list identification numbers assigned to the site. Enrolled children will then undergo a baseline assessment. The baseline assessment includes data collection on demographics and socioeconomic status, anthropometric assessments, and a malaria rapid diagnostic test (RDT; see Figure 1 and Section 3 for details). After completion of the baseline assessment,

children will be randomized to receive either a single dose of directly observed oral azithromycin or a 7-day course of oral amoxicillin.

The randomization sequence will be generated by the UCSF investigators using R (R Foundation for Statistical Programming, Vienna, Austria). Children will be randomized in a 1:1 fashion to a single dose of azithromycin or a short course of oral amoxicillin. The randomization sequence will be linked to the study identification numbers. Randomized study arm assignments will be placed in sealed, opaque envelopes labeled with study identification numbers. When a child has been enrolled and has completed the baseline assessments, a CSPS nurse trained for the study will open the envelope to determine the allocation, and will administer study medication indicated as described in Sections 2.4 and 4.

To keep the allocation concealed, only the study nurse administering treatment will have access to the envelopes with the randomization allocations. The study nurse will open the envelope and administer treatment in a private room without the outcome assessor present. For each enrolled child, the study nurse will record whether or not azithromycin was administered on a paper form kept in a locked cabinet not accessible by the outcome assessor.

Given the nature of the intervention, participants and study personnel administering treatment will not be masked to treatment assignment. Outcome assessors will be masked to treatment assignment; this will be accomplished by assigning one CSPS nurse to administer treatment and a separate masked study team member to perform outcome assessments, including anthropometry, malaria RDT, and vital status updates.

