### Secondary Outcomes

- **Nutritional recovery by 8 weeks (Specific Aim 2).** Nutritional recovery will be defined as a child having WHZ  $\geq -2$  on two consecutive visits and no acute complication or edema for the past 7 days OR MUAC of  $\geq 125$ mm on 2 consecutive visits and no acute complication or edema for the past 7 days. The criteria chosen to define the recovery will be the same one we used to admit the child into the program.

- **Time to recovery.** Time from enrollment to nutritional recovery (defined above) will be calculated in days by subtracting the date of enrollment from the date of nutritional recovery.
- **Nonresponse at 8 weeks.** Nonresponse will be documented if a child does not meet the criteria for nutritional recovery at 8 weeks.
- **Transfer to inpatient care.** The occurrence, date, and reason for transfer from outpatient to inpatient treatment will be recorded.
- **Mortality by 8 weeks.** Vital status will be assessed at all follow-up time points and mortality will be defined as death during the study period. Date of death will be recorded.
- **Clinical signs of infection.** At all follow-up time points, clinical signs of infection will be recorded, including care-giver reported experience of fever, diarrhea, vomiting, and respiratory infection/cough and clinical diagnoses made at by site personnel
- **Adverse events.** Adverse events will be reported at all follow-up time points (defined in Section 5).
- **HAZ.** Height or length will be measured at all follow-up time points and height-for-age z-scores will be calculated.
- **MUAC.** Mid-upper arm circumference will be measured at all follow-up time points.
- **WAZ.** Weight will be measured at all follow-up time points and weight-for-age z-scores will be calculated.
- **WHZ.** Weight and height, assessed at all follow-up time points, will be used to calculate weight-for-height z-scores.
- **Malaria.** Rapid diagnostic tests for malaria will be conducted at baseline and week 8 to determine malaria infection status.
- **Intestinal microbiome:** Rectal swabs will be collected in a random subset of children at baseline and at week 8.

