### **3.6. Clinical examination**

Outcomes of clinical examinations will be collected at enrollment, weekly follow-up visits, and at week 8. Clinical examinations will be conducted according to the standard of care in the management of SAM. Recorded outcomes include diagnoses made and treatments given/recommended.

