## 5. ADVERSE EVENTS

Parents or guardians of enrolled children will be instructed to report any adverse events experienced within the 7 days following the enrollment visit, by phone or in person. At all follow-up visits, study staff will inquire about the child's experience of adverse events, including if the child had any of the following symptoms:

- Fever
- Diarrhea
- Vomiting
- Abdominal pain
- Skin rash
- Constipation

The study team will assess whether the parent or guardian sought care for the child since the last visit and if so, what the reason was for the health care visit and if the child was hospitalized.

Serious adverse events will be defined as death, hospitalization, or any other life-threatening situation. Serious adverse events will be reported to the Medical Monitor within 24 hours. The study team member conducting the follow-up visit will email the CRSN Principal Investigator, who will immediately email the Medical Monitor and the UCSF study team. The Medical Monitor will make a determination as to whether the event could be reasonably considered to be related to the study drug and will report the results of this determination to the study investigators and the DSMC as needed. Information on all adverse events, serious and non-serious, will be recorded on data collection forms through the mobile application.

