### **Secondary outcomes.**

Time to event outcomes (time to recovery and time to mortality) will be assessed visually using Kaplan-Meier curves and compared by arm using the log-rank test.

Binary outcomes will be analyzed using modified Poisson regression for rare outcomes (e.g. mortality) or log-binomial regression for common outcomes (e.g. malaria), using models similar to the one described above for Specific Aim 2.

Anthropometric assessments will be analyzed using linear models as described for Specific Aim 1, with correction for baseline values. For anthropometric assessments, z-scores will be calculated based on the 2006 WHO Child Growth Standards. Anthropometric z-scores will be analyzed as continuous variables and secondary analyses will explore categorization.

All analyses will be intention-to-treat. A significance level of 0.05 for inference and 95% confidence intervals will be reported for all effect estimates. All analyses will be conducted using R (R Foundation for Statistical Computing, Vienna, Austria). For all models, model diagnostics will be conducted to assess appropriate fit.

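### The legible text has no pre-dose symptom question and no new-or-worse rule, so mild illness present before dosing can be counted as an adverse event or infection sign

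*Combined protocol and SAP*

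**What the plan says.** - **Adverse events (Section 5).** "At all follow-up visits, study staff will inquire about the child's experience of adverse events", with a list of fever, diarrhea, vomiting, abdominal pain, skin rash and constipation. Caregivers are also told to "report any adverse events experienced within the 7 days following the enrollment visit". The only look-back window at the visit belongs to a different question, whether the caregiver "sought care for the child since the last visit". The symptom list has no onset date and no worsening test.
- **Infection signs (Section 2.5, secondary outcomes).** "At all follow-up time points, clinical signs of infection will be recorded, including care-giver reported experience of fever, diarrhea, vomiting" and respiratory infection or cough, together with diagnoses by site personnel. The same list names baseline explicitly for malaria and for rectal swabs.
- **Baseline (Section 2.3).** "The baseline assessment includes data collection on demographics and socioeconomic status, anthropometric assessments, and a malaria rapid diagnostic test". Symptom history is not listed.
- **What is recorded at entry.** Section 3.6: "Outcomes of clinical examinations will be collected at enrollment, weekly follow-up visits, and at week 8", meaning diagnoses and treatments. Section 3.3 takes a temperature with the malaria test, which is done at baseline and week 8.
- **Eligibility (Section 2.2).** Only complications needing antibiotics or inpatient care exclude a child, so milder fever, diarrhea, vomiting or cough does not.
- **Analysis (Section 9.2).** "Anthropometric assessments will be analyzed using linear models as described for Specific Aim 1, with correction for baseline values". Binary outcomes follow the Specific Aim 2 model, whose only covariate is treatment arm.

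**The concern.** Section 1.1 describes children with SAM as carrying a heavy infectious burden, so some will probably enter with a mild symptom. If the symptom is still present at the week 1 visit, the plan as written records it both as an adverse event and as a sign of infection. The data then cannot separate it from a symptom that began after the dose. The enrollment diagnoses and temperature give a partial baseline, but no planned analysis of these outcomes uses them, and neither measures caregiver-reported diarrhea, vomiting, abdominal pain or constipation.

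Two things are at stake. First, Section 2 calls this a pilot for a larger trial, and the symptom rates it reports would be higher in both arms than the rates arising after dosing. Second, cases unrelated to the drug that are added equally to both arms make a real difference in tolerability harder to see. The first week is also the period Section 5 singles out for caregiver reporting.

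**Working it through.** **The plan's own figure.** None exists for these outcomes; Section 9.1 covers weight gain and recovery only. The power formula used below was checked on Aim 2: 66% vs 81% with 135 per arm gives 80.1%, matching the stated 80%.

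**Inputs from the documents.** 135 analysed per arm (the 270 in the Section 9.1 commands, split 1:1) and alpha 0.05, taken as two-sided.

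**Assumptions, not in the documents.** New-onset risk r is 20% in one arm and 10% in the other. Carry-over b is the share of children with the symptom at entry who still report it at week 1. It is equal in both arms and runs from 2% to 40%.

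**Formulas.**
- Risk as written: b + (1 − b)r.
- New onset only, all children in the denominator: (1 − b)r.
- New onset among children symptom-free at entry: risk r, with 135(1 − b) per arm.
- Power = Φ[(d − 1.96·SE0)/SE1], where d is the risk difference, SE0 uses the pooled risk and SE1 the separate risks.

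Example at b = 30%. As written: 0.30 + 0.70 × 0.20 = 0.44 and 0.30 + 0.70 × 0.10 = 0.37, ratio 1.19. New onset: 0.14 and 0.07, ratio 2.0.

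| b | Risks as written | RR | Power | New-onset risks | RR | Power (all 135) | Power (symptom-free only) |
|---|---|---|---|---|---|---|---|
| 0% | 20.0 vs 10.0% | 2.00 | 63% | 20.0 vs 10.0% | 2.0 | 63% | 63% |
| 2% | 21.6 vs 11.8% | 1.83 | 58% | 19.6 vs 9.8% | 2.0 | 62% | 63% |
| 10% | 28 vs 19% | 1.47 | 41% | 18 vs 9% | 2.0 | 58% | 59% |
| 20% | 36 vs 28% | 1.29 | 29% | 16 vs 8% | 2.0 | 53% | 54% |
| 30% | 44 vs 37% | 1.19 | 21% | 14 vs 7% | 2.0 | 47% | 49% |
| 40% | 52 vs 46% | 1.13 | 16% | 12 vs 6% | 2.0 | 41% | 43% |

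The risk difference shrinks by the factor (1 − b), from 10 points to 6 at b = 40%.

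**If existing illness clears at different rates.** Let 20% be ill at entry.
- Persistence of 80% in the higher-risk arm and 50% in the other: 0.20 × 0.80 + 0.80 × 0.20 = 32% against 0.20 × 0.50 + 0.80 × 0.10 = 18%. The difference grows from 10 to 14 points and power rises from 63% to 76%, although the ratio is 1.78.
- Persistence reversed: 26% vs 24%, ratio 1.08.
- New-onset risks of 30% vs 20% with persistence of 80% and 50%: 40% vs 26%, ratio 1.54, above the new-onset ratio of 1.5.

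The direction therefore depends on clearance.

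**Would a baseline covariate repair it?** Under the equal carry-over model, modified Poisson regression with the baseline symptom added returns 1.83, 1.47, 1.29, 1.19 and 1.13, the same as unadjusted. The covariate is balanced across arms, so the fitted arm ratio must equal the ratio of total events. For b of 10% to 40%, a log-binomial fit is held at about 1.0, because carry-over children already sit at probability 1 in both arms. Only a change in which cases are counted restores 2.0.

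**The case against.** **Absence is not proven.** Section 2.3 refers to Figure 1 and Section 3 for details, and Section 6.1 to Figure 1 and Section 2.5. Figure 1 survives only in part, and the study forms in Appendix 2 are not shown. The surviving fragment lists hemoglobin, which neither Section 2.3 nor Section 2.5 mentions, so those lists are not complete. This stands: a baseline symptom item may exist. It would not supply the missing new-or-worse rule or the missing use of baseline status in the analysis.

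**Stronger readings a reader might infer.**
- *That nothing about illness is recorded before dosing.* Sections 3.6 and 3.3 contradict this. Site diagnoses, one part of the infection-sign outcome, already have an enrollment value.
- *That the comparison is biased between arms.* Randomization balances pre-existing illness in expectation, and leaving out a baseline covariate does not by itself invalidate the comparison.
- *That any drug difference is necessarily diluted.* That needs equal persistence. The randomized comparison is between two antibiotics, so clearance of existing illness may itself differ by arm, and the documents do not fix the direction.

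**The consequence is limited.** These are secondary outcomes with no stated power, and even new-onset counting reaches only 41% to 62% in the table. Eligibility screening and the appetite test may keep carry-over small; at 2% the loss is slight. The effect fades after the early visits. Serious events have their own definition and a relatedness review by the Medical Monitor. All of this stands and sets the priority.

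**Conclusion.** The gap is real in the legible text. Caregiver symptom questions are scheduled at follow-up, with no listed pre-dose counterpart, no new-or-worse definition and no planned use of the enrollment information for these outcomes. The consequence that holds however the drugs act on existing illness is that reported symptom rates include illness that predates the dose. Attenuation of the arm comparison is conditional on equal persistence.

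The size cannot be derived, because the documents give no symptom prevalence or new-onset rate. The tabulated range rests wholly on the assumed 20% vs 10%, on equal carry-over, and on a single early visit. It shows that the effect runs from negligible at 2% carry-over to large at 30% or 40%. This is an inexpensive improvement of minor priority.

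**What to change.** 1. **Baseline form.** Check Figure 1 and the form. If the items are not there, ask the same yes/no symptom questions before the envelope is opened. There are seven distinct items: the six in Section 5 plus respiratory infection or cough.
2. **Section 5.** Count a symptom as an adverse event only if it was absent at baseline or is reported as worse since dosing, and add one follow-up item on worsening. Leave serious adverse event reporting unchanged.
3. **Section 9.2.** Analyse each caregiver-reported infection sign as new onset among children without that symptom at baseline, and also report the all-cases comparison, which captures any difference in clearance. Adding the baseline symptom as a covariate is not enough on its own. For clinical diagnoses, use the enrollment examination already recorded under Section 3.6.

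The cost is about seven form items, the worsening item and a sentence or two in each section, with no new procedure or staff. The downsides are reliance on the caregiver's judgement of worsening and a smaller denominator for new onset. That denominator also loses children whose entry symptom would have resolved. Baseline symptoms cannot be recovered reliably later, so the change is useful only for children not yet enrolled.

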## **6. DATA COLLECTION, MANAGEMENT, AND SECURITY**

### **6.1. Data Collection**

Data will be collected on enrolled children at baseline (time of enrollment), and follow-up weeks 1- 8. Written informed consent will be collected on paper and the study nurse will record treatment administration on paper. All other data will be collected electronically on mobile devices using the Interviewer mobile application by Survey Solutions. Data to be collected are outlined in Figure 1 and Section 2.5.

### **6.2. Data Management and Security**

Electronic data will be uploaded daily to a secure, password-protected, cloud-based server hosted by Survey Solutions. All devices used for data collection will be password-protected, as will the mobile application itself. Paper forms will be stored in locked cabinets accessible only by specific study team members at each enrollment site.

No identifiers will be collected electronically. Study data will only be accessible by study team members and investigators in order to protect confidentiality.

### **6.3. Data Quality and Monitoring**

All study team members collecting data will undergo an initial training to learn how to use the mobile devices as well as best practices for data collection. Data collection will be monitored on a weekly basis by the study team using dashboards created on Survey Solutions web-based platform. Concerns over data quality and completeness will be relayed to the local study team by email, and refresher trainings and/or additional supervision of data collection by local investigators will be planned as needed. The study team will send quarterly progress reports to the DSMC, including aggregate data on enrollment and follow-up status, weight gain, nutritional recovery, and adverse events.

## **7. PROTECTION OF HUMAN SUBJECTS**

Before any study procedures are implemented, the study team will obtain Institutional Review Board (IRB) approval from committees at UCSF and CRSN. In addition, local study team members will approach each potential enrollment site to describe the study and obtain their consent to participate as a study site. At the individual level, study personnel will obtain written informed consent from at least one parent or guardian for all study activities. If, at any time, a parent or guardian elects to withdraw a child from the study, they will be free to do so. Individuals who withdraw will be offered the same standard of care outside the study.

### **7.1. Institutional Review Board Approval**

#### **University of California, San Francisco (UCSF) Committee on Human Research**

UCSF's Committee on Human Research will annually review the study protocol for ethical approval.

#### **Comité d'Ethique du Burkina Faso**

The study protocol will be reviewed and granted ethical approval by the Comité d'Ethique du Burkina Faso in Nouna before any study activities begin.

### **7.2. Informed Consent**

Study personnel fluent in relevant local languages will approach parents or guardians of eligible children at the enrollment site. In a private setting, the study team member will explain the objectives, risks, and benefits of the study as well as detailed information about what study participation entails for the child and the parent or guardian. The study team member will clarify that participation in the study is voluntary, that participation may be stopped at any time, and that all collected data will be kept confidential and securely stored. The study team member will ensure comprehension by inviting the parent or guardian to ask questions and will provide time for the parent or guardian to consider participation. When providing consent, both the study team member and the parent or guardian will sign two copies the consent document. One copy will be given to the parent or guardian and the other will be kept for study reference.

## **8. DATA AND SAFETY MONITORING COMMITTEE**

The Data and Safety Monitoring Committee (DSMC) will consist of independent experts in biostatistics, epidemiology, child health and nutrition, and/or global public health.

The DSMC will be empaneled prior to the beginning of the study. The committee will meet once prior to the start of the study and at the study's conclusion. All study protocols will be subject to review and approval by Institutional Review Boards at UCSF and CRSN, and by the DSMC. Serious adverse events will be reported to the DSMC based on the determination of the Medical Monitor. Committee members will monitor any severe or unexpected trend that threatens the safety of study participants. Quarterly progress reports will be submitted to the DSMC. Enrollment progress will be reviewed after 1 month to assess feasibility. Stopping guidelines will be agreed upon prior to the start of the study, and the DSMC will be authorized to end the study if they deem necessary.

## 9. STATISTICAL METHODS

### 9.1. Sample Size and Power

**Specific Aim 1** We assume that inclusion of 300 children (150 randomized to each arm) will provide 80% power to detect a 27% increase in weight gain (g/kg/day) in children receiving azithromycin compared to children receiving amoxicillin at an alpha of 0.05. Assumptions for this calculation were based on the pattern of weight gain reported in a trial of routine amoxicillin for uncomplicated SAM in Niger comparing children receiving amoxicillin to placebo over time. We assumed an average weight gain of 4.9 g/kg/day in the amoxicillin arm, with a standard deviation of 3.9 g/kg/day, and loss to follow-up of 10%. A 27% increase corresponds to a mean difference in weight gain of 1.3 g/kg/day, or an average weight gain of 6.2 g/kg/day in the azithromycin arm.

This calculation was performed in Stata using the following command:

```
power twomeans 4.9, sd(3.9) alpha(0.05) power(0.8) n(270)
```

**Specific Aim 2.** Inclusion of 300 children (150 randomized to each arm) will provide 80% power to detect an 15 percentage point difference in the proportion of children achieving nutritional recovery in the azithromycin arm compared to the amoxicillin arm. Assumptions for this calculation were based on nutritional recovery reported in the amoxicillin arm of a trial of routine amoxicillin for uncomplicated SAM in Niger. We assumed that 66% of children in the oral amoxicillin arm would achieve nutritional recovery and a loss to follow-up of 10%.

This calculation was performed in Stata using the following command:

```
power twoproportions 0.66, alpha(0.05) power(0.8) n(270)
```

### 9.2. Statistical Analysis

**Baseline characteristics.** Characteristics of the study population collected at baseline will be summarized using frequencies and percentages for categorical variables and means and standard deviations or medians and inter-quartile ranges for continuous variables. Baseline characteristics will be compared by treatment arm using Fisher's exact test for categorical variables and t-tests or Wilcoxon rank-sum tests for continuous variables.

**Specific Aim 1.** The primary analysis will compare weight gain velocity (g/kg/day) between groups over the 8-week follow-up period,. We will estimate mean differences and 95% confidence intervals for the difference using a linear regression model with an indicator for study group.

$$E[Y | X = x] = \beta_0 + \beta_1 X + e$$

Where:

- $Y$  = weight gain velocity from enrollment to 8 weeks
- $X$  = binary indicator for treatment group ( $X=1$  for azithromycin,  $X=0$  for a short course of oral amoxicillin)
- $\beta_1$  = difference in weight gain velocity between the azithromycin group compared to a short course of oral amoxicillin group

- $e \sim N(0, \sigma^2)$

**Specific Aim 2.** The primary analysis will compare nutritional recovery by 8 weeks from baseline by arm. We will use log-binomial regression for this analysis to estimate the risk ratio. We will use the following model:

$$\log[P(Y = 1|X_1 = x_1)] = \beta_0 + \beta_1 X_1 + e$$

Where:

- $Y$  = binary indicator for nutritional recovery by 8 weeks ( $Y=1$  for recovered,  $Y=0$  for not recovered)
- $X$  = binary indicator for treatment arm ( $X=1$  for azithromycin,  $X=0$  for a short course of oral amoxicillin)
- $e^{\beta_1}$  = relative risk of nutritional recovery in azithromycin arm compared to a short course of oral amoxicillin arm
- $e \sim N(0, \sigma^2)$

If the log-binomial model fails to converge, we will use a modified Poisson model with robust standard errors as an alternative.

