### **Missing data.**

If  $\leq 10\%$  of enrolled children is missing outcome data, complete case analyses will be conducted. If  $>10\%$  of enrolled children are missing outcome data, inverse probability weighting will be used to weight complete cases by the inverse of an estimate of the probability of an outcome being observed as a sensitivity analysis. Weights will be constructed with the following baseline characteristics chosen as factors likely to predict follow-up: SES, distance from CSPS, WHZ, and MUAC.

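### The primary weight-gain model contains treatment arm only; a short prespecified list of baseline covariates already collected could narrow its confidence interval at almost no cost.

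*Combined protocol and SAP*

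**What the plan says.** Under Specific Aim 1, Section 9.2 estimates the mean difference in weight gain velocity "using a linear regression model with an indicator for study group". The displayed equation has an intercept and one binary term for arm. No adjusted version, primary or supportive, is described for this outcome.

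Three other places bear on the choice:

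- **Section 9.2, Secondary outcomes:** "Anthropometric assessments will be analyzed using linear models as described for Specific Aim 1, with correction for baseline values". This sentence covers HAZ, WAZ, WHZ and MUAC. It adds a term to the Aim 1 model and does not change that model.
- **Section 9.2, Missing data:** the inverse probability weights use the "following baseline characteristics chosen as factors likely to predict follow-up: SES, distance from CSPS, WHZ, and MUAC".
- **Section 2.3:** "The baseline assessment includes data collection on demographics and socioeconomic status, anthropometric assessments, and a malaria rapid diagnostic test". All of this is completed before the allocation envelope is opened. No stratification factor is stated.

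Section 9.1 sizes the trial as an unadjusted comparison of two means: control mean 4.9, SD 3.9, alpha 0.05, 80% power, 300 children randomized and 270 evaluable after 10% loss. It states a detectable increase of 27%, or 1.3 g/kg/day.

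**The concern.** In a linear model, adding prognostic baseline covariates leaves the target of estimation unchanged (the mean difference between arms) and removes from the residual variance whatever they explain. If age, sex and nutritional status at entry predict weight gain, the arm-only model gives a wider interval and less power than the collected data allow. The secondary anthropometric outcomes get a baseline-adjusted model and the primary outcome does not.

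The sample size has little slack. Section 9.2 also plans significance tests of baseline characteristics by arm but does not say what follows if an imbalance appears. An adjustment added after seeing such tests could look data-driven; a list fixed now could not. The trial is described in Section 2 as a pilot for a larger one, and an adjusted model would also supply the residual variance needed to size that trial.

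The point concerns weight gain only. The recovery outcomes are also unadjusted but are not considered here.

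**Working it through.** **Inputs from Section 9.1.** SD 3.9; 300 × 0.9 = 270 evaluable, 135 per arm; alpha 0.05; power 80%. Sidedness is not stated in words. Two-sided is assumed, because it reproduces the stated figure and one-sided does not (at a difference of 1.3, one-sided power would be 86.3%).

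**Reproducing the plan's figure.** By the normal formula, detectable difference = 3.9 × √(2/135) × (1.960 + 0.842) = 1.330 g/kg/day, and 1.330/4.9 = 27.1%. By noncentral t with 268 degrees of freedom it is 1.335. Both match the stated 27%. The stated 1.3 is this figure rounded down; at exactly 1.3 the t-test power is 77.9%.

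**Unadjusted precision.** SE = 3.9 × √(2/135) = 0.4747. The 95% half-width is 1.969 × 0.4747 = 0.935.

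**Adjusted precision.** For k covariate terms explaining a share R² of within-arm variance:

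SE = 3.9 × √[(1 − R²) × (2/135) × 267/(267 − k)], with 268 − k degrees of freedom.

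The last factor is the expected variance inflation from fitting k covariates (1 when k = 0), so the cost of the covariates is counted. R² is not in the documents; the range 0 to 0.30 is an assumption.

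Results for k = 4 (age, sex, WHZ, MUAC):

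| R² | Detectable difference at 80% power | Power at 1.335 | 95% half-width | Equivalent evaluable N |
|---|---|---|---|---|
| Unadjusted | 1.335 | 80% | 0.935 | 270 |
| 0 | 1.345 | 79% | 0.942 | 266 |
| 0.05 | 1.311 | 81% | 0.918 | 280 |
| 0.10 | 1.276 | 83% | 0.893 | 295 |
| 0.20 | 1.203 | 87% | 0.842 | 332 |
| 0.30 | 1.125 | 91% | 0.788 | 380 |

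Equivalent N is 270 × (1.3347 / adjusted detectable difference)². For R² = 0.20: 270 × (1.3347/1.2029)² = 332.

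**Break-even.** The adjusted and unadjusted detectable differences are equal at R² = 0.015 for four terms. At R² = 0 the loss is 1.345 − 1.335 = 0.010 g/kg/day.

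**Longer list.** With k = 10 the detectable differences at the same R² values are 1.361, 1.326, 1.291, 1.217 and 1.138, and break-even rises to R² = 0.038. Extra terms that add no explained variance only cost precision.

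**Check of the formula.** Simulating the fitted model (20,000 trials per setting, three normal covariates and one binary, true difference 1.335) gave power of 79.0%, 81.4%, 83.4%, 87.2% and 91.4% across the five R² values. R² is an input to this simulation, so it confirms the formula and says nothing about which R² will occur.

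**The case against.** The plan is coherent as written. It is powered on an unadjusted SD and analysed without adjustment, no stratification factor demands adjustment, and a simple comparison is a reasonable choice for a pilot. All of that is true, and it is why this is not called an error. Sizing on the unadjusted SD is nevertheless compatible with an adjusted analysis.

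The stronger objection is that the benefit rests on an R² that no document supplies. There are reasons to expect a low value: entry requires WHZ below −3 or MUAC below 115 mm, which restricts the range of both, and the outcome is already a change scaled per kg. At R² = 0.05 the detectable difference falls by only 0.024 g/kg/day. The larger gains need R² of 0.20 or more. This stands as a limit on size.

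The supporting passages also do not show that these covariates predict weight gain. The secondary models correct for baseline values of the measurements, and the weighting variables were chosen to predict follow-up. That stands too: those passages show that the data exist and that adjustment is acceptable to the planners, not that it will pay. The width of the planned interval proves nothing either. A half-width of about 70% of the detectable difference (0.935/1.335) follows from choosing 80% power at two-sided 5%.

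Finally, Section 9.2 sits inside the combined protocol, and Section 8 makes protocols subject to IRB and DSMC review, so the change may carry an approval step. None of these points removes the asymmetry: a small, bounded expected loss against a possible material gain.

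**Conclusion.** The concern holds as an efficiency improvement worth making. The arm-only analysis is valid. Adding four prespecified terms costs about 0.01 g/kg/day of detectable difference if they explain nothing, and helps once they explain more than about 1.5% of within-arm variance. At R² of 0.10 the detectable difference falls from 1.335 to 1.276, equivalent to about 25 more evaluable children (295 against 270); at 0.20, about 62 more (332 against 270).

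These figures assume the plan's SD of 3.9, 135 evaluable children per arm, a two-sided test, and an R² within the assumed range of 0 to 0.30. The actual gain cannot be known from the documents and may be small.

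**What to change.** Before anyone involved in the analysis sees outcome data by arm, amend Section 9.2, Specific Aim 1, so that the primary model is linear regression of weight gain velocity on arm plus four baseline terms: age, sex, WHZ and MUAC. Report the arm-only model as a prespecified sensitivity analysis. Keep the list this short. Site is optional, because Section 2.3 describes identification lists by site but not randomization stratified by site.

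A lighter alternative is to leave the arm-only model primary and prespecify the adjusted model as supportive. That removes the risk of a data-driven adjustment, but the primary interval does not benefit.

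The cost is a change of wording, with whatever IRB and DSMC review an amendment of the combined document requires. No new data are needed: anthropometry and demographics are collected before allocation, and sex is taken to be part of demographics. Statistically it uses four of 268 degrees of freedom. The sample size calculation can stay as it is.
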